10.6 Definition of Positive Detection Accuracy

The Positive Detection Accuracy (PDA) is defined as PDA = k/n, where *n* is the number of the total DOIs in FAS-Cohort 1 (malfunction sessions have been excluded from FAS-Cohort 1), and k is the number of total positive detections by the patch.

10.7 Definition of Detection Latency

As shown in the system diagram in Figure 1, there are 4 time-stamped events (TSEs) associated with measuring detection latency shown in Table 3.

Table 3: Time-stamped events (TSEs) associated with measuring detection latency

| TSE 1 | Subject takes tablet. Directly observed ingestion time is recorded by the clinician. |
|-------|--|
| TSE 2 | Tablet sends signal to the patch. Tablet is detected & recorded by the patch as an IEM record with a timestamp. |
| TSE 3 | Patch sends ingestion data to phone. The tablet ingestion data is communicated to and recorded by the mobile device as a pill-ingestion-metric with a timestamp. |
| TSE 4 | Tablet ingestion data is displayed. The tablet display event is triggered on the mobile device as a pill-display-event with a timestamp. |

Figure 1: Digital Medicine System

The latency measurements between each of above timestamps are defined in Table 4.

Table 4. Latency measurements

| Table 4. Datency m | casul cilicitis | |
|--------------------|-----------------|---------------|
| CCI | | Page 11 of 20 |
| | | Page 11 of 20 |

Strictly Confidential. © 2023, PRA Health Sciences. All rights reserved.

Statistical Analysis Plan (SAP) Version Date: 22-JUN-2023 Sponsor: Otsuka Pharmaceutical Development & Commercialization, Inc. Protocol No: 031-201-00521

| Latency Measurements | Definition | Maximum Observation Time |
|---------------------------------|---|-----------------------------|
| Patch Detection Latency | Time between TSE 1 and TSE 2 in seconds | 10 minutes/600 seconds |
| Ingestion Data Transfer Latency | Time between TSE 2 and TSE 4 in seconds | 5 minutes/300 seconds |
| Total Detection Latency | Time between TSE 1 and TSE 4 in seconds | 15 minutes/900 seconds |

For Kaplan-Meier estimate, if the DOI is successfully detected, it will be treated as positive detection and event = "1"; If the DOI is not successfully detected or latencies have been larger than the maximum observation time (defined above in Table 4), the data will be considered as censored data and event = "0", where time to event is defined as maximum observation time.

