10.8 Missing Data

All statistical analysis will be based on observed values. Missing values will not be imputed.

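### The Kaplan-Meier event in SAP 10.7 is tied to patch detection for all three latencies, which misfits the two that end at display: Total is flattered if displays are missed, and Transfer can err either way

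*SAP*

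**What the plan says.** SAP 10.7 (Table 3) lists four time stamps: TSE 1 is the observed ingestion, TSE 2 detection by the patch, TSE 3 receipt by the phone, and TSE 4 display. For TSE 4, "The tablet display event is triggered on the mobile device as a pill-display-event with a timestamp". Table 4 defines Patch Detection Latency as TSE 1 to TSE 2 (cap 600 s), Transfer as "Time between TSE 2 and TSE 4 in seconds" (cap 300 s) and Total as "Time between TSE 1 and TSE 4 in seconds" (cap 900 s).

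One rule then covers all three: "For Kaplan-Meier estimate, if the DOI is successfully detected, it will be treated as positive detection and event" = 1. The censoring half reads "If the DOI is not successfully detected or latencies have been larger than the maximum observation time (defined above in Table 4"), and such records get event = 0, "where time to event is defined as maximum observation time". SAP 10.6 counts positive detections as detections by the patch. SAP 10.8 adds: "All statistical analysis will be based on observed values. Missing values will not be imputed".

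SAP 12.5.2 plots the three latencies as three curves per cohort and tabulates survival status, median and quartiles. It takes TSE 2 to TSE 4 from the phone download. Protocol 8.10.1 and SAP 12.5.1 take positive detections from the same source.

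**The concern.** The event is defined by a step that comes before the end point of two of the three measures. That leaves two gaps.

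- **Detected but not displayed (TSE 2 present, TSE 4 absent).** The event rule makes this an event. It is not undetected, and it has no latency to compare with 300 or 900 s, so neither censoring condition plainly applies. With no imputation, standard software would drop it for want of a time.
- **Not detected (no TSE 2).** The rule censors this at 300 s on the Transfer curve, although the transfer clock never started. A patch failure is then counted as a transfer failure.

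The latencies are primary endpoints, and display is the last step of the system under test. PDA stops at patch detection and covers Cohort 1 only, and the descriptive latency statistics use observed times only. The Kaplan-Meier analysis is therefore the one planned summary that could count a detected but undisplayed tablet as a failure.

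**Working it through.** **Inputs.** The documents give no figure for this point. From the sample size text (Protocol 9.1, SAP 8.1): 24 × 15 = 360 ingestions in Cohort 1 and an assumed PDA d = 0.973 (0.973 × 360 = 350.28, so 350 detected). Cohort 2 has 30 ingestions; I assume 29 detected. The share t of detected tablets never displayed is my assumption, shown over a range. I also assume no malfunction exclusions and no latency beyond its cap.

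**Formulas.** All censoring falls at the cap, after every event, so the height of each curve at the cap is a simple proportion.

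- Total, true share displayed: d(1 − t).
- Total and Transfer as written, undisplayed records dropped: d(1 − t) / [d(1 − t) + 0.027].
- Transfer, target among detected tablets (the clock starts at TSE 2): 1 − t.

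| t | As written (both curves) | Total, true | Transfer, target |
|---|---|---|---|
| 1% | 0.9633/0.9903 = 97.3% | 96.3% | 99.0% |
| 3% | 0.9438/0.9708 = 97.2% | 94.4% | 97.0% |
| 5% | 0.9244/0.9514 = 97.2% | 92.4% | 95.0% |

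The curve as written hardly reacts to t. Total is too high at every t above 0. Transfer is too low at 1%, nearly right at 3% and too high at 5%. It is right when d(1 − t) + 0.027 = d, so 1 − t = 0.946/0.973 and t is about 2.8%.

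**Whole counts.**

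| Cohort, undisplayed | As written | Total, missing TSE 4 censored | Transfer, detected only |
|---|---|---|---|
| 1, 0 | 350/360 = 97.2% | 350/360 = 97.2% | 350/350 = 100% |
| 1, 7 (2%) | 343/353 = 97.2% | 343/360 = 95.3% | 343/350 = 98.0% |
| 1, 18 (5%) | 332/342 = 97.1% | 332/360 = 92.2% | 332/350 = 94.9% |
| 1, 35 (10%) | 315/325 = 96.9% | 315/360 = 87.5% | 315/350 = 90.0% |
| 2, 1 | 28/29 = 96.6% | 28/30 = 93.3% | 28/29 = 96.6% |
| 2, 3 | 26/27 = 96.3% | 26/30 = 86.7% | 26/29 = 89.7% |

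**Reported quantiles.** The Kaplan-Meier p-quantile is roughly the (p × n / displayed) quantile of the displayed times. With 18 undisplayed in Cohort 1:

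- Median: as written 0.5 × 342/332 = 0.515; Total corrected 0.5 × 360/332 = 0.542; Transfer corrected 0.5 × 350/332 = 0.527.
- 75% point: 0.75 × 342/332 = 0.773; 0.75 × 360/332 = 0.813; 0.75 × 350/332 = 0.791.

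So the median shifts by one to three percentiles of the displayed times, and the 75% point by two to four.

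**If the cap is read to censor undisplayed records.** Total is then correct. Transfer becomes d(1 − t): 96.3%, 94.4% and 92.4% against targets of 99.0%, 97.0% and 95.0%. Even at t = 0 it shows 97.3% instead of 100%, because undetected ingestions stay in its risk set.

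**The case against.** - **The cap may already cover the case.** A tablet not displayed by 300 or 900 s has, on an ordinary time-to-event reading, exceeded the limit. Censoring is not imputation, and SAP 10.7 already gives the maximum time to undetected ingestions, which have no end time either. This is a fair reading and may be what is intended. It is not what the text says, since a missing latency is not a larger one, and two programmers could derive different curves. It also leaves the Transfer risk set wrong.
- **Not every transfer failure is lost.** A reader might infer that failed transfers in general vanish from the curves. The documents do not support that. Detections and TSE 2 to TSE 4 come only from the phone, so a complete patch-to-phone failure appears as not detected and is censored on all three curves. A late display is censored by its cap. Only a record that reached the phone without a display time stamp is exposed. Table 3 separates TSE 3 from TSE 4, so this state can exist, but nothing says how often.
- **The case is not invisible.** The Cohort 1 listing (SAP 12.3.1) has a detected flag and a display time. The Cohort 2 listing (SAP 12.3.2) has no flag but gives both detection and display times. The number at risk would also fall. This stands, although no planned table counts these ingestions.
- **Small effect on what is reported.** The endpoint is the median (Protocol Table 3-1) or the mean and median (SAP 9.1), the SAP calls the study exploratory, and no latency threshold is set. This stands at low failure rates.

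**Conclusion.** The event rule fits Patch Detection Latency and misfits the other two measures. Dropping undisplayed records is an inference from an incomplete rule, not something the SAP states.

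On that literal reading, Total errs in the device's favour by about 1, 3 and 5 percentage points at assumed display-failure rates of 1%, 3% and 5%. A reader might infer that Transfer is flattered too. That does not follow: below a failure rate of about 2.8% the undetected ingestions pull it under its target, and only above that rate is it too high.

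The sizes rest on 97.3% detected, on assumed display-failure rates, and on taking detected tablets as the proper base for Transfer. The effect lies mainly in the upper part of the curves and the number at risk. It is worth correcting before the analysis because it concerns primary measures, but it does not touch PDA and is unlikely to change the medians much.

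**What to change.** In SAP 10.7, replace the single rule with one for each measure:

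- **Patch:** event if TSE 2 occurs within 600 s of TSE 1; all ingestions in the analysis set.
- **Transfer:** event if TSE 4 occurs within 300 s of TSE 2; only ingestions with a TSE 2.
- **Total:** event if TSE 4 occurs within 900 s of TSE 1; all ingestions in the analysis set.

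State that a missing or late end time stamp is censored at that measure's cap, and that this is not imputation under SAP 10.8. In SAP 12.5.2, add the number detected but not displayed, by cohort, and a footnote that Transfer has a smaller risk set than the other two curves.

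The cost is a few lines of SAP text and derivation code, with no new data. Total becomes slightly less favourable if displays are missed; Transfer may move either way. The change cannot separate a complete patch-to-phone failure from non-detection, because both reach the analysis as no record.

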8.10 Other Assessments

8.10.1 Positive Detection Accuracy

The number of total DOIs will be reported by the site on the eCRF. Positive detections will be downloaded from the trial mobile device(s) for analysis.

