9.2.3 Full Analysis Set

The **Full Analysis Set (FAS)** comprises all the detections of the wearable sensors done on the subjects who took at least 1 dose of MITs (Cohort 1) or Abilify MyCite (Cohort 2), excluding those detections with device malfunction (invalid session and impedance is bad).

For the primary endpoint in Cohort 1, the **FAS-Cohort 1** is a subset of the FAS and consists all the detections for subjects who took at least 1 dose of MITs (Cohort 1).

For the primary endpoint in Cohort 2, the **FAS-Cohort 2** is a subset of the FAS and consists all the detections for subjects who took at least 1 dose of Abilify MyCite (Cohort 2).

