12.5.2 Detection Latency Measures

As defined in **Table 3**, the directly observed ingestion time (TSE 1) is recorded in the CRF. Other signal detection times (TSE 2-4) will be downloaded from the trial mobile device(s) for analysis. The derivation of detection latency measures, including Patch Detection Latency, Ingestion Data Transfer Latency, and Total Detection Latency, are provided in **Table 4**.

The three detection latency measures for all DOIs will be summarized using descriptive statistics, for **FAS-Cohort 1** and **FAS-Cohort 2** separately.

Furthermore, two Kaplan-Meier curves will be plotted for all of the latency times (all DOIs), for **FAS-Cohort 1** and **FAS-Cohort 2** separately. The three detection latency measures will be displayed as three curves on the plot. A table will be provided to show the summary of survival status, the median (50% survival time), and 25% and 75% percentiles of survival by Kaplan-Meier estimate.

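### The single Kaplan-Meier rule in SAP 10.7 censors DOIs with no TSE 2 at 300 s in the Ingestion Data Transfer Latency curve, although that interval starts at TSE 2 (minor)

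*SAP*

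**What the plan says.** SAP 10.7 (Table 3) defines TSE 2 as the patch's own time-stamped record of the tablet and TSE 4 as the display on the phone. Table 4 defines Ingestion Data Transfer Latency as "Time between TSE 2 and TSE 4 in seconds" and sets its maximum observation time at 300 s. Patch and Total Detection Latency both start at TSE 1, the observed ingestion.

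One Kaplan-Meier rule follows, with no distinction between the three measures. On the event side, "if the DOI is successfully detected, it will be treated as positive detection and event" is set to 1. On the censoring side, "If the DOI is not successfully detected or latencies have been larger than the maximum observation time", event is set to 0 and the time is the maximum in Table 4.

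SAP 12.5.2 states that "two Kaplan-Meier curves will be plotted for all of the latency times (all DOIs"), with transfer latency as one of three curves on each cohort's plot. A table gives "the summary of survival status, the median (50% survival time), and 25% and 75% percentiles of survival by Kaplan-Meier estimate". The same section also summarises all three latencies with ordinary descriptive statistics.

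The Full Analysis Set in SAP 9.2.3 is formed by "excluding those detections with device malfunction (invalid session and impedance is bad"). On the data source, SAP 12.5.2 says "Other signal detection times (TSE 2-4) will be downloaded from the trial mobile device(s) for analysis", and Protocol 8.10.1 says "Positive detections will be downloaded from the trial mobile device(s) for analysis".

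**The concern.** A tablet that the patch never detected was never at risk of having its data transferred. Its transfer interval has no time origin. The rule nevertheless gives it 300 s of event-free follow-up, so a failure of the tablet-to-patch step is displayed as a failure of the patch-to-phone step. The transfer curve then levels off above zero even if every transfer that began was completed promptly, and its 25/50/75% points are read too far out in the distribution.

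There is also a wording gap. The event side of the rule depends on detection, and the rule does not expressly cover a DOI with a TSE 2 but no TSE 4. That is the record that most clearly belongs in the transfer analysis as censored.

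What is at stake is how one of the three component curves is interpreted, mainly in Cohort 2, where a single miss is 3.3% of the data and no PDA is planned. The same rule is sound for Patch and Total Detection Latency, because every DOI has a TSE 1.

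**Working it through.** **Do undetected DOIs reach the transfer curve?** SAP 9.2.3 describes the Full Analysis Set in terms of detections, which could be read as detected DOIs only. Three places rule that out. SAP 10.6 takes n, the total DOIs for PDA, from FAS-Cohort 1, so a set of detected DOIs would make PDA 100% by construction. SAP 12.3.1 lists a true/false detection field for that set. SAP 12.5.2 says all DOIs, for both cohorts. The censoring clause for undetected DOIs would also have nothing to act on. Only malfunction records leave the set; other misses stay.

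**Inputs.** Cohort 1: 360 DOIs and an assumed PDA of 97.3% (Protocol 9.1, SAP 8.1). Cohort 2: 30 DOIs, with no detection rate given. Maximum observation time for transfer: 300 s (SAP 10.7).

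**The plan's own figure.** Expected detections are 360 × 0.973 = 350.28. The Clopper-Pearson 95% lower limit there is 95.05%, which matches the stated 95%. At whole counts it is 94.95% with 350 detections (10 misses) and 95.31% with 351 (9 misses). The plan's rate therefore corresponds to about 10 misses, and a Cohort 1 of 360 DOIs that meets the criterion of a lower limit above 95% has at most 9.

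**Formula.** All censoring is at 300 s, so before 300 s the Kaplan-Meier estimate equals the empirical survival over the DOIs included. Suppose u of n DOIs have no TSE 2 and all u are patch misses. Then:

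- floor of the curve = u/n
- the reported p% point is the p × n/(n − u) % point of detected DOIs (valid while that point lies below 300 s)

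| u/n | Floor | Reported 25/50/75% points are, among detected DOIs |
|---|---|---|
| 9/360 | 2.5% | median: 50 × 360/351 = 51.3% |
| 10/360 | 2.8% | 25.7 / 51.4 / 77.1% (× 360/350) |
| 1/30 | 3.3% | median: 50 × 30/29 = 51.7% |
| 2/30 | 6.7% | median: 50 × 30/28 = 53.6% |
| 3/30 | 10.0% | 27.8 / 55.6 / 83.3% (× 30/27) |

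The Cohort 2 counts are assumptions that show the range.

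**In seconds (illustration only).** The documents give no latency distribution. Assume lognormal transfer times with median 30 s and log-SD 0.5 to 1.0. The reported quantile is 30 × exp(log-SD × z), where z is the normal quantile of the shifted point.

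- 10/360: the median moves from 30 s to 30.5–31.1 s.
- 3/30: the median moves to 32.2–34.5 s, and the 75% point to 48.7–78.9 s, against 42.0–58.9 s among detected DOIs.

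**If some DOIs without a TSE 2 are failed transfers.** Let m of the u be true patch misses, with m from 0 to u. The correct denominator is n − m. The SAP curve's median is then the 50 × n/(n − m) % point, and a curve restricted to DOIs with a TSE 2 gives the 50 × (n − u)/(n − m) % point. For 10/360 these run over 50.0–51.4% and 48.6–50.0%. For 1/30 they run over 50.0–51.7% and 48.3–50.0%. The two curves bracket the truth.

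**The case against.** Several stronger readings are tempting, and the documents do not support them.

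- **That the primary latency endpoint is biased.** SAP 9.1 names the mean and median. Only the descriptive summary yields both; the Kaplan-Meier table has no mean. Protocol 9.4.1 likewise has summary statistics for the latencies and curves as plots. The most natural reading is that the endpoint is descriptive. Those statistics use observed values (SAP 10.8) and are untouched.
- **That every detected DOI counts as an event.** The second clause of the rule censors latencies above the maximum, so a detected DOI with a transfer longer than 300 s is censored. A missing TSE 4 fits that clause naturally, so this gap is one of wording.
- **That times lengthen in proportion to the misses.** The percentile rank scales with the miss share; the time does not. In the illustration, 2.8% misses lengthen the median by about 1.8–3.6%.
- **That the floor is certainly false.** Detections and TSE 2–4 come from the phone. A tablet that the patch recorded but never transferred may also appear as having no TSE 2, and for that record censoring at 300 s is right.

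The opposing case also says that the effect is small and largely visible already, and this stands. Ignoring clustering, the standard error of the illustrative Cohort 1 median is about 1.253 × 30 × log-SD/√350 = 1.0–2.0 s, roughly twice the shift. If the 97.3% rate is carried to Cohort 2 (an assumption), the chance of no misses is 0.973^30 = 44% and of three or more is 4.6%. The patch curve sits on the same plot, the listings show detection and display times, and the study is described as exploratory with no latency threshold. None of this gives the undetected DOIs a time origin.

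**Conclusion.** The point holds as a minor correction. As written, SAP 10.7 and 12.5.2 together place DOIs with no TSE 2 in a curve whose clock starts at TSE 2, and no other section removes them.

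The size depends on how many DOIs lack a TSE 2 and on how many of those are patch misses. If all are misses, Cohort 1 at the plan's rate has a curve that is 2.8% too high at its end and a median 1.4 percentage points out in rank. Cohort 2 could be further out, but only with miss counts that the documents do not predict. The upper quartile and the end of the curve move more than the median. The statements in percentile rank need no distributional assumption; those in seconds rest entirely on the assumed lognormal.

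**What to change.** **SAP 10.7**, for Ingestion Data Transfer Latency only: include DOIs with a TSE 2; set event = 1 if TSE 4 follows within 300 s; otherwise, including when there is no TSE 4, set event = 0 at 300 s. Leave the rule for Patch and Total Detection Latency unchanged.

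**SAP 12.5.2**: state the number of DOIs in each curve. Label the transfer curve as conditional on a patch record having reached the phone, and report beside it the number of DOIs with no TSE 2. Keep the all-DOI transfer curve as a sensitivity display.

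**Cost**: a few SAP sentences, a label, a count and one extra display, with no new data and no protocol change. The downside is that the restricted curve is slightly optimistic if some transfers failed completely. The count and the sensitivity display disclose this.

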10.8 Missing Data

All statistical analysis will be based on observed values. Missing values will not be imputed.

11.0 Interim Analyses

No interim analysis is planned in this study.

12.0 Statistical Methods

All analyses will use SAS® version 9.4 or higher. Table and listing outputs will be presented using ICON standard layouts.

Unless specified otherwise, categorical variables will be summarized using counts and percentages (n [%]). Percentages will be rounded to one decimal place, except 100% will be displayed without any decimal places and percentages will not be displayed for zero counts.

Continuous variables will be summarized using the number of observations (n), mean, and standard deviation, median, minimum, and maximum. The minimum, and maximum values will be displayed to the same level of precision as the raw data; the mean and the median to a further decimal place; and the standard deviation to two additional decimal places to a maximum of four.

In listings, data will be presented with the same precision as the original data.

Unless specified otherwise, all the tables will be produced by cohort, and overall will not be displayed.

Unscheduled visits will not be summarized or included in any analysis but will be included in listings outputs.

12.1 Subject Disposition

The following information will be summarized for subject disposition by cohort in table based on **SCR** Analysis Set:

• Number and percentage of subjects screened,

Page 12 of 20

Strictly Confidential. © 2023, PRA Health Sciences. All rights reserved.

- Number and percentage of screening failures and corresponding reasons for screening failure,
- Number and percentage of subjects included in each analysis set (EAS, FAS, and SAF).

Furthermore, following information will be provided by cohort in tables based on EAS.

- Number and percentage of subjects who complete all the ingestions,
- Number and percentage of subjects who complete study,
- Number and percentage of discontinuations from study and corresponding reasons for discontinuation,

The following reasons - as specified in the CRF - will be included in the disposition tables and in a listing (Listing: Enrollment and Study Completion for **SCR** Analysis Set):

Reasons for Screening Failure:

- 1. Failed Inclusion Criteria
- 2. Met Exclusion Criteria
- 3. Death
- 4. Adverse Event
- 5. Physician Decision
- 6. Pregnancy
- 7. Protocol Deviation
- 8. Terminated by Sponsor
- 9. Withdrawal by Subject
- 10. Other

Reasons for Study Discontinuation:

- 1. Death
- 2. Adverse Event
- 3. Lost to Follow-up
- 4. Non-compliance with Device/Patch
- 5. Physician decision
- 6. Pregnancy
- 7. Protocol Deviation
- 8. Terminated by Sponsor
- 9. Withdrawal by Subject
- 10. Withdrawal of Consent

Strictly Confidential. © 2023, PRA Health Sciences. All rights reserved.

11. Other

